8.1.1. Study medication

This study is designed as a phase Ib 8 week monocentric, randomized, double-masked, vehicle controlled, parallel groups study (referred to as the controlled treatment period) followed by a 24 week follow-up period (4 weeks masked follow-up and additional 20 weeks unmasked follow-up).

The 60 consecutively enrolled patients will be randomized in a 2:1 ratio to the active treatment arm (rhNGF 180 µg/ml, one drop TID) or to the vehicle arm (vehicle, one drop TID) during the 8 week treatment period.

On the Day 0 Visit the first 2 doses (1 dose = 1 drop) of study medication will be administered in the clinic by study site personnel and the patient will be monitored for adverse events. In the absence of any clinically significant side effects in the opinion of the investigator the patient will be dispensed their study medication and instructed to self-administer the 3rd dose of Day 0 at home 6 hours after the 2nd dose of study medication was given. The patient will also be instructed to return to the study clinic after 1 week for Week 1 Visit.

Patients enrolled in the study will continue their 8 week treatment and will later enter the 24 week follow-up period without interruption.

8.1.2. Other medications

Upon enrolment, the previous topical glaucoma medications of patients will be continued normally, however, it will be required that previous topical ophthalmic medications used for intraocular pressure control will not be changed during the course of the study. Any other topical ocular treatment not related to intraocular pressure control for glaucoma, that is used before enrollment, will need to be discontinued and patients will only be allowed to use the study medication provided by Dompé and preservative-free artificial tears during the course of randomized controlled treatment period.

No rescue medication is planned for this study.

8.2. 24 WEEK FOLLOW-UP PERIOD

At the conclusion of the controlled treatment period at Week 8, patients will be discontinued from study treatment. During the 24 week follow-up period (Weeks 9-32) the patients will be followed without any protocol required study medication, however, preservative-free artificial tears (not provided by Dompé) may be prescribed as needed as at the discretion of the study investigator.

The first 4 weeks of the follow up period will be referred to as masked follow-up (and patients treatment will be kept masked) while the following 20 weeks will be referred to as unmasked follow-up (patients treatment will be unmasked at week 12) and the database will be locked. The database will be locked and the study will be complete after the last randomized patient has completed 4 weeks of the follow up period (Week 12 Visit). However, after the database lock patients still in the follow up period will continue with scheduled visits for the remainder of the 24 week follow up period.

9. INVESTIGATIONAL PRODUCT

9.1. IDENTITY OF STUDY TREATMENT

The Test product is a form of recombinant human Nerve Growth Factor (rhNGF) produced in *E.coli* developed by Dompé R&D Laboratories. rhNGF is a sterile 0.18 mg/mL single use lyophilized preparation, packaged in a glass vial, and administered after reconstitution with 0.3 ml of sterile WFI contained into a glass prefilled syringe. The WFI prefilled syringe is used with an adaptor consisting of a connecting device with dual connections: one end for the glass-syringe and one end for the vial. The drug product will be manufactured under environmental and process aseptic conditions in accordance with GMP guidelines to obtain a final sterile drug product.

Test product: Recombinant human nerve growth factor 180µg/ml (one 35 µl drop equals to 6.30 µg of rhNGF) reconstituted solution

Vehicle Control: Ophthalmic Placebo solution of the same composition as the test product with the exception of rhNGF reconstituted solution

Investigational product will be provided as a 4-weeks kit formed by two boxes: the first box containing the vials (lyophilized product) and the second box containing adaptors and prefilled 0.3 ml WFI syringes. Each vial after reconstitution contains a volume of 0.3 ml rhNGF 180 µg/ml or control. A training manual for investigators with detailed instructions on how to reconstitute the eye drops from the lyophilized product is provided in Appendix A.

The clinical labeling of the investigational product will be done in a manner that protects the masking of the study medication. It will include a statement of caution and describe particulars applicable to regulatory requirements (e.g.: kit number, protocol number, storage conditions, name and address of the sponsor, statement that the product is for investigational use only, etc.).

9.1.1. Dose Selection Rationale

The rationale for the rhNGF eye drops solution dosages to be investigated in this study (180 µg/ml) is derived from the results of *in vivo* pharmacology studies, preclinical safety and toxicity studies and a phase I, randomized, double-masked, vehicle-controlled study of rhNGF in healthy volunteers demonstrating no significant ocular or systemic safety concerns with the proposed therapeutic dose.

In a preclinical models, we have investigated the effective dose-regimen of rhNGF by measuring the activation of the high affinity NGF receptor as well as apoptosis biomarkers expressed in the retina of rats with inherited retinal degeneration and with an induced damage of the optic nerve (partial optic nerve transection).

Among the different rhNGF dose regimen tested, only the dose of 180µg/ml given three times a day for three consecutive days induced significant activation of the NGF receptors well as downregulation of pro-apototic biomarkers. Additionally, published reports of patients with advanced optic neuropathies treated with mNGF 200 µg/ml 3 or 4 times a day for variable time periods showing visual function improvements provide objective human evidence that topically applied NGF can achieve pharmacologically active concentrations in the back of the eye. In a preclinical study utilizing radiolabeled rhNGF to investigate the disposition of rhNGF in the eye of the 3 concentrations evaluated (20, 50 and 200 µg/ml) only the 200 µg/ml dose was detectable in the back of the eye. So, while it is clear that topically applied NGF can reach the back of the eye and exert a therapeutic effect, based on the available preclinical and clinical data it is currently unclear which concentration of topical rhNGF will yield the most effective treatment benefit in patients with glaucoma. Therefore, the objective of this study is to assess the safety and potential efficacy of a 180 µg/ml rhNGF treatment to determine its safety for use in subsequent phase 2 and 3 clinical trials in this indication.

9.1.2. Treatment Dispensing and Dosing

Eligible patients will be randomized and randomization numbers will be assigned to the patients by the investigator in ascending sequential order. Each eligible subject will be assigned to a randomization number according to the sequence of study entry, from 01 to 60. Randomization code break envelopes will be provided to the Investigator with the IMP in the event unmasking is required.

The patients will be dispensed a 4 week supply of study medication on the Day 0 visit and at Weeks 4 as shown in Table 9.1.2-1.

**Table 9.1.2-1 - Kit Assignments**

| Weekly visit | # of kits |
|---|------------------|
| Day 0 - Randomization / Therapy initiation Visit | 1 kit |
| Week 4 Visit | 1 kit |

Study medications that will be dispensed to the patient during the study visits will be distributed in refrigerated bags. In addition to the study medication to be administered in the clinic on the day of the study visit, patients will also be instructed to bring back to the clinic at each study visit all the used and unused vials by placing them in the refrigerated bag that was given at the Day 0 visit (so that it can be used for dispensing the next kit, if applicable).

Each 4 week kit will be composed of 1 box containing a total of 90 single-use vials of the randomized / assigned medication for daily treatment during 4 weeks and 1 box containing the same number of adaptors and prefilled 0.3 ml WFI syringe.

All patients will be dosed one drop (35 µl) three times a day (TID) in each eye during the 8 weeks, randomized, double-masked, controlled treatment period.

9.1.3. Usage

All study drugs used in this study are for topical ocular usage only. Dispensing of the study medications to the patients will be performed as described in Section 9.1.2 and table 9.1.2-1.

All patients will be dosed one drop (35 µl) TID in each eye every morning, afternoon and evening as shown in the **Table 9.1.3-1**. The timing of instillation should be adjusted if a patient's awakening and/or bedtime differs.

Patients will begin treatment in the clinic at the Day 0 visit, where he/she will be shown how to resuspend the lyophilized molecule and instill the eyedrops in the eyes. For this purpose, a training manual with detailed instructions on how to reconstitute the eye drops will be provided to the investigators (see Appendix A). Patients will then be instructed to self-administer the study medication one drop three times a day through 8 Weeks of the controlled treatment period. During the 8 week controlled treatment period patients will be instructed to return to the clinic on the monthly visits with the used kits and empty (used) vials as well as

with the daily kit of study medication and vials to be used on the day of the study visit in the refrigerated bag that will be given when the study medication is dispensed.

Table 9.1.3-1. – Dosing Schedule

| TREATMENT | TREATMENT DOSING SCHEDULE |
|-----------------------------------|--------------------------------|
| rhNGF 180 µg/ml or Vehicle | Morning (approximately 8 AM) |
| | Afternoon (approximately 2 PM) |
| | Evening (approximately 8 PM) |

9.1.4. Precautions of Use

In rats and rabbits no evidence of systemic toxicity was observed following treatment with intravenous rhNGF at doses up to 2.4 mg/kg. In the same species, no local ocular toxicity was observed following treatment with topical rhNGF eye drops at concentrations up to 1.2 mg/ml. In a phase I, randomized, double-masked, vehicle-controlled study of rhNGF in healthy volunteers no ocular or systemic toxicity was demonstrated in patients administered topical rhNGF up to 180 µg/ml 3 times a day for 5 days. Being a recombinant protein, rhNGF it is not expected to be mutagenic, therefore, reproductive toxicity and teratogenicity studies have not been performed. However, as a precaution, the investigational product should not be handled by pregnant females, should be kept away from children and contact with the skin or mucosae other than that for required for topical ocular administration should also be avoided. In case of accidental spills or contact cleanse/wash the exposed area with tap water and soap.

**9.1.5. Storage**

Investigational product must be stored in a secure area at the investigational site as per the labeling instructions. A temperature probe and data logger will accompany the drug on shipment. It is essential that the Investigational sites verify the temperature range reached during shipment, so that potential stability concerns during shipment can be discovered and appropriate action taken. The box of the investigational product containing the lyophilized preparation must be stored at 2-8°C at the Investigational sites (preferably at the pharmacy of the hospital), whereas the box containing the prefilled syringes and adaptors may be kept at room temperature. Eligible patients will receive the first 4-week kit of study medications in a refrigerated bag containing the investigational product. The vehicle control will be also dispensed in a refrigerated bag. The patient will be instructed to store the study medication (the box of the investigational product containing the lyophilized preparation) at home in the refrigerator at 2-8 °C for the entire 4 weeks until next visit. The box containing the prefilled syringes and adaptors may be kept at room temperature. When the patients will start to use the study medications at home each day they will remove from the refrigerator only the vials to be used over the course of the day. Patients will use one vial to instill one drop in both eyes three times per day.

A daily temperature log will be maintained at the site for documenting appropriate storage conditions and will be made available for the study monitor to inspect. Any deviations from the recommended storage conditions should be immediately reported to Dompé and the use of the drug suspended until authorization for its continued use has been given by Dompé.

Investigational products will be supplied as a lyophilized preparation in glass vials together with a prefilled 0.3 ml sterile WFI syringes and adaptors. The vials will be labeled with the appropriate clinical study labeling. The vehicle of rhNGF will be supplied in glass vials identical to those containing rhNGF with a prefilled 0.3 ml WFI syringes and adaptors. The vials containing the vehicle will be labeled with the appropriate clinical study labeling. Investigational product will be kept in an identical box to ensure double-masking.

9.1.6. Accountability Procedures

Upon receipt, the study staff designated by the Investigator will inventory the clinical investigational products, and complete and sign the Receipt of Clinical Study Investigational products Section of the appropriate form in use. A copy of the form will be maintained in the Investigator's records and the original will be provided to the CRO, delegated by Dompé.

The designated study staff must keep a complete and accurate accountability of all investigational products used on the investigational products Dispensing Log. In no case will the investigational products be used in any unauthorized situation. Investigational products returned to the Dompé for destruction will be recorded in the Return of Clinical Investigational products Form. These records will be made available to the study monitor for the purpose of accounting for all study investigational products. The study monitor will account for all investigational products. It is the Investigator's responsibility to ensure the reconciliation of study medications at the conclusion of the study. Any discrepancies and/or deficiencies in study drug accountability must be recorded along with an explanation.

Investigational product which has been dispensed to a patient and returned unused will not be re-dispensed to a different patient.

Unused investigational products must not be discarded or used for any purpose other than the present study. Any remaining investigational products at the end of the trial will be returned to Dompé or disposed of as determined by Dompé for destruction.

9.1.7. Assessment of Compliance

Patient compliance with the study medication will be assessed at each study visit following the dispensing of the study medication for self-administration. Compliance with the study medication dosing schedule will be verified by the monitor during on-site monitoring visits, as per records in the eCRF, versus accountability records.

9.1.8. Patient Confidentiality and Methods Used to Minimize Bias

During the 8 week, randomized, double-masked controlled treatment period the study treatments will be unknown to the patient, the Investigator and the site staff. The identity of the treatments will remain unknown to the patient, Investigator, site staff and Dompé's clinical research personnel until the study is unmasked after the last enrolled patient completes week 12 visit (end of the masked follow-up) and the database is locked, except in case of specific events that will require unmasking of the patient(s).

The vials of rhNGF (180µg/ml) and the vials containing the vehicle of rhNGF will be identical in appearance and the contents of the vials will be indistinguishable. Dompé and CRO Biostatistics staff who are directly involved in the analysis of study results will remain masked to treatment assignments until the end of the masked follow-up.

A list of sequential kit numbers will be generated by a member of the CRO SAS programming group not involved in the conduct of the study. Each kit number will be randomly associated with a treatment group. Patients will be assigned to treatment in numerical order. A tear-off label from the kit box, with the kit number, will be attached to the investigational product dispensing log.

If the Investigator becomes unmasked for any reason, this information will be recorded on source data and in the eCRF of the study, specifying the date and the reason.

In the event of a medical emergency where the knowledge of patient treatment is required to provide the patient with appropriate care, Investigators will have the possibility to unmask the treatment assignment for a specific patient. See Paragraph 12.5 for information on unmasking procedure.

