10. STUDY PROCEDURES

10.1. OUTLINE OF STUDY

The study will be conducted as a 8 week monocentric, randomized, vehicle controlled, double-masked, parallel groups study followed by a 24-week follow-up period. The study will be considered completed when the last enrolled patient completes their final study visit at Week 32 of the follow-up period.

The 8 week controlled treatment period will include 7 scheduled clinical evaluation visits: Baseline Screening Visit, Day 0-Therapy Initiation Visit, Week 1, Week 4, Week 8, Week 12 and 32 Visits. Week 1 Visit has a window of ± 2 days, Week 4 Visit has a window of ± 4 days, while Week 8, 12, 32 Visits have a window of ± 7 days, at the discretion of the investigator, required procedures for a scheduled visit may be performed over 2 consecutive days

10.1.1. 8 Week Randomized, Double-Masked Controlled Treatment Period

Enrolled patients will be randomized at baseline in a 2:1 ratio to the active treatment arm (rhNGF 180 $\mu\text{g/ml}$ three times a day in both eyes) or the vehicle during the 8 week controlled treatment period as shown in the following table:

| Treatment Arms | Treatments |
|----------------|--|
| 1 | 180 $\mu\text{g/ml}$ rhNGF one drop three times a day in both eyes |
| 2 | Vehicle one drop three times a day in both eyes |

At the conclusion of the randomized, double-masked, controlled treatment period all patients will discontinue the study medication and enter a 24 week follow-up period (4 weeks masked follow-up and additional 20 weeks unmasked follow-up).

10.1.2. 24 Week Follow-Up Period

During the 24 week follow-up period, patients will be followed without any protocol required study medication; however, preservative-free artificial tears (not provided by Dompé) may be prescribed as needed at the discretion of the study investigator.

Two clinical evaluation visits are foreseen at week 12 and 32.

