11. ANALYSIS PLAN

The primary objective of the study is to assess the safety and tolerability of a 180µg/ml TID dose regimen of recombinant human nerve growth factor (rhNGF) eye drop solution administered over 8 weeks versus a vehicle control in patients with progressive primary open-angle glaucoma despite IOP control.

The secondary objectives are to measure the changes in BCDVA, visual field, ERG and structural changes in changes in ganglion cell layer and nerve fiber layer thickness measured by optical coherence tomography. The secondary outcomes will be examined at 1, 4 and 8 weeks of therapy, and at 4 and 24 weeks after cessation of therapy (Week 12 visit and Week 32 visit), and will include functional assessments to investigate evidence of a persistent biological effect after discontinuation of the study treatment.

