9.2 Final Analysis

At the end of the study (i.e. after all patients have completed Week 32 Visit), an updated analysis will be performed presenting the complete study data. Section 12 indicates which TLFs will be reproduced because they will contain additional data from the period after the first 12 weeks until Week 32. These newly produced TLFs will be reported in a Statistical Report that is to be considered as an addendum to the CSR.

10 Overview of Tables, Listings and Figures

In this section, TLFs will be presented content wise. The full set of TLFs will be tabulated in section 12, where it will also be indicated whether the item is unique (or first mentioned) or a repeat. Mock shells for unique TLFs will be presented in a separate document.

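### Patients and site staff learn the allocation after Week 12 for no stated reason, so some or all Week 32 acuity and USPON assessments are made unmasked and reported without a split

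*Protocol*

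**What the plan says.** **When masking ends.** Protocol 9.1.8 says who is masked ("The identity of the treatments will remain unknown to the patient, Investigator, site staff and Dompé's clinical research personnel") and for how long ("until the study is unmasked after the last enrolled patient completes week 12 visit (end of the masked follow-up) and the database is locked"). Section 12.5 repeats this rule, which is one calendar event for the whole study. Section 8.2 adds a parenthesis, "patients treatment will be unmasked at week 12", that can be read as each patient's own Week 12. It also expects patients to be at different stages at the lock: "after the database lock patients still in the follow up period will continue with scheduled visits". Section 10.1.1 describes the follow-up as "4 weeks masked follow-up and additional 20 weeks unmasked follow-up", and the title of Section 10.2.6 places Week 32 in the unmasked part.

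**What happens after Week 8.** No study drug is given: in Section 10.1.2, "patients will be followed without any protocol required study medication". No crossover, extension or procedure that depends on the arm is described.

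**How Week 32 is used.** Protocol 11 wants "functional assessments to investigate evidence of a persistent biological effect after discontinuation of the study treatment", and Week 32 is the only scheduled visit after Week 12. SAP 7.2.7 defines USPON, a primary safety outcome, from Yes/No ticks on the acuity, visual field, ERG and OCT pages at any time after first dose, so Week 32 counts. SAP 9.2 says "an updated analysis will be performed presenting the complete study data". SAP Section 12 marks Table 14.2-1.1 (primary safety outcomes) and the acuity, PhNR and OCT change summaries for repetition in that analysis. None is divided by whether the assessment was masked.

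**The concern.** The Week 12 analysis needs unmasked data, but that requires only the analysts to know the allocation. No passage gives a reason for telling patients, the investigator or the site while Week 32 visits are outstanding.

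Two things recorded at Week 32 are sensitive to that knowledge. Acuity depends on patient effort. USPON is an investigator's tick. Protocol 12.1.6 gives a numeric limit for the acuity route but none for the visual field or optic nerve routes. The visual field tick matters more than it first appears: under SAP 3.6 and 10.7.2 visual fields are otherwise only listed, so this judgement is the only field result that reaches a summary table.

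Expectation is plausible. Protocol 11.4 describes the product as already shown to be safe and effective at this dosage. Section 12.4.3 recognises the risk in another setting: because the trial is small and single-centre, the investigator is told of SUSARs in blinded form.

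At stake is whether a Week 32 difference in acuity or in late USPON reflects a lasting effect of the drug or knowledge of the arm.

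**Working it through.** The documents state no figure for this, so there is nothing to reproduce. The timeline gives the size.

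**Inputs.**
- 60 patients (Protocol synopsis).
- 32 − 12 = 20 weeks between the Week 12 and Week 32 visits (study plan).
- Accrual period A weeks and delay c weeks from the last Week 12 visit to the lock. Neither is in the documents; both are assumed.
- Uniform accrual, all 60 attending Week 32, and ±7-day windows ignored. Dropout would lower the counts.

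**Reading 1: one unmasking at the lock (Sections 9.1.8 and 12.5).** Unmasking falls at A + 12 + c. A patient starting at time t has Week 32 at t + 32, which is unmasked if t + 32 > A + 12 + c, that is, t > A − 20 + c. Hence

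unmasked share = min(1, (20 − c)/A).

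Examples with c = 4: A = 26 gives 16/26 = 0.615, and 0.615 × 60 ≈ 37. A = 12 gives 16/12 = 1.33, capped at 1, so 60.

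Week 32 visits made unmasked, of 60:

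| A (weeks) | c = 0 | c = 4 | c = 8 |
|---|---|---|---|
| 12 | 60 | 60 | 60 |
| 20 | 60 | 48 | 36 |
| 26 | 46 | 37 | 28 |
| 40 | 30 | 24 | 18 |
| 52 | 23 | 18 | 14 |
| 78 | 15 | 12 | 9 |

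Masked and unmasked Week 32 visits are mixed whenever A > 20 − c. All 60 are unmasked only if the single site enrols at least 60/(20 − c) patients per week: 3.0, 3.75 or 5.0 for c = 0, 4 or 8. The last patient's Week 32 is unmasked for any c below 20.

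**Reading 2: each patient at their own Week 12 (Section 8.2).** All 60 Week 32 visits are unmasked whatever A and c are. Nothing is mixed, but the exposure is complete. SAP 9.1 lets post-Week 12 primary safety data into the main analysis, so late USPON ticks there would be unmasked too.

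**What is exposed.**

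| Item | Exposure at Week 32 |
|---|---|
| Acuity score and logMAR | Yes: effort-dependent, in repeated change tables |
| USPON ticks, including visual field | Yes: judgement, in final Table 14.2-1.1 |
| PhNR, OCT thickness | Less: instrument readings |
| Visual field values | Listed only |
| VAS tolerability | None: last scheduled at Week 12 |
| Two investigator-flagged AE outcomes | Little: SAP 7.2.7 expects them only during treatment |
| USPON during treatment period | None: ends at Week 8 |
| Inferential tests (SAP 8.2, 8.3) | None: Week 8 or earlier, not rerun for the final analysis |

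**The case against.** The unmasked period is a disclosed choice. The synopsis announces it, and open follow-up after treatment is a common trade-off in a Phase Ib study with no formal sample size. Protocol 11.5.1 has follow-up data described without testing. Table 14.2-1.1 already carries a row for USPON during treatment, which is fully masked. Substantial worsening of acuity is derived by threshold, separately for treatment and follow-up (SAP 7.2.9). Under Sections 9.1.8 and 12.5, everything in the Week 12 lock was recorded before general unmasking, so only the later addendum to the study report is exposed. Comparing the two runs of Table 14.2-1.1 would also give a rough separation of late USPON.

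Most of this stands, and it limits the reach of the point. A reader might infer that the primary safety incidences as a whole, or the main analysis, are open to bias. The documents do not support that: the exposure is narrow and lies after Week 12.

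A reader might also infer that site unmasking has no possible later use. SAP 3.6 leaves mitochondrial redox reporting to the investigator, and a comparison by arm there would eventually need the allocation. No document says it is needed before the last Week 32 visit.

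What the objection does not answer is the missing split. The caution in SAP 9.1 to focus on results before Week 12 concerns preliminary data in the main analysis, not the final one. SAP 7.2.1 counts a patient as unmasked only if the emergency envelope was opened. Week 32 acuity cannot be separated by comparing runs, because main-analysis visit tables stop at Week 12.

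**Conclusion.** The point holds within limits. Some or all Week 32 acuity measurements and USPON ticks will be made with known allocation, for no stated reason, and will be reported without distinction. Over the assumed ranges (A from 12 to 78 weeks, c from 0 to 8) this is 9 to 60 of 60 visits under Sections 9.1.8 and 12.5, and all 60 if Section 8.2 means each patient's own Week 12. These counts rest on assumed accrual and lock delay; only the 20-week gap comes from the documents.

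It is tempting to say that masked and unmasked visits will certainly be pooled. That requires both the lock-date reading and accrual slower than the rates above, so it cannot be asserted. Week 8 inference, VAS and treatment-period USPON are unaffected, as is the Week 12 main analysis under the lock-date reading. This is a worthwhile, cheap improvement to the persistence and late-safety evidence, not a defect in the main result.

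**What to change.** 1. Reconcile Protocol 8.2 with 9.1.8 and 12.5 so that one unmasking rule applies.
2. Amend those sections so that only the sponsor/CRO analysis team is unmasked at the Week 12 lock. Patients, the investigator and site staff stay masked until the last patient's Week 32 visit, with the emergency code break unchanged. Investigator-led redox reporting by arm waits until then. The synopsis, Sections 8.1.1 and 10.1.1 and the title of 10.2.6 need matching edits.
3. If site unmasking is kept, add to SAP 9.2 a flag by date of unmasking, and show masked and unmasked Week 32 acuity and post-Week 12 USPON in separate rows. Assessments are dated, and Section 9.1.8 already requires the date of any investigator unmasking in the eCRF, so the flag needs little new data.

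Step 2 takes unmasked Week 32 assessments to 0 of 60, apart from emergency code breaks, and changes no sample size, alpha or visit. Its cost is protocol wording, an access list for the Week 12 output, and a delay of up to about 20 weeks before the allocation and patient-level Week 12 results reach the site.
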